### **Adverse Events of Interest**

Adverse events of interest are defined in a version-controlled Product Safety Analysis Plan (PSAP) for talimogene laherparepvec. The search terms of each event of interest (EOI) will be extracted based on the most recent version of the PSAP prior to the database snapshot for the analysis. Versions of the PSAP and MedDRA used for the EOI analysis will be documented in clinical study report(s). All the safety analysis of talimogene laherparepvec adverse events of interest (EOI) and pembrolizumab events of clinical interest (ECI) will be evaluated in each monotherapy and combination cohorts in Part 1 (by cohort/group) and each tumor type separately in Part 2 (by tumor type/group). The subject incidence of treatment-emergent and treatment-emergent, treatment-related EOIs and ECIs (including all events of interest, serious events of interest, non-serious events of interest) according to the EOI search strategy categories and ECI categories will be summarized.

In addition, EOI and ECI may be tabulated by worst grade within EOI category and ECI category by preferred term respectively. A table summarizing the incidence of all treatment-emergent adverse events of interest will also be provided by EOI category and ECI category as a high level summary.

### **Subject Incidence of Detectable Talimogene Laherparepvec in Blood and Urine**

The analysis will be based on the Blood Evaluable Analysis Set in which proportions of subjects that meet the criteria of detectable (defined as positive result by qPCR analysis) DNA in blood will be calculated. The point-wise exact 95% confidence intervals for binomial proportions using the F-distribution ([Leemis and Trivedi, et al, 1996](#)) from SAS® PROC FREQ procedure with the binomial option will also be calculated. Similar analysis of incidence of talimogene laherparepvec DNA detected in the urine will be repeated using the Urine Evaluable Analysis Set.

A detailed listing of qPCR results for subjects with detectable talimogene laherparepvec DNA per qPCR timepoints during the first 4 cycles and safety follow-up will be provided.

The analysis will be based on available cases; that is, subjects who do not have blood sample (or urine sample for respective analysis) collected at the respective time points will be excluded from the analysis for that time point.

### **Incidence of Clearance of Talimogene Laherparepvec DNA in Blood and Urine**

The number and proportion of subjects with undetectable talimogene laherparepvec DNA per qPCR in blood among subjects with sample collected in each cycle will be presented. Incidence of clearance of talimogene laherparepvec DNA from Cycle 1, 2 and 3 in blood will be calculated by cycle. The exact 95% CI for the binomial proportions using the F-distribution will be calculated. The analysis of clearance of talimogene laherparepvec in the blood will include subjects in the Blood Clearance Analysis Set. The analysis will be repeated using the Urine Clearance Analysis Set to evaluate clearance in the urine.

In addition, the analysis of incidence of clearance at Day 8 ( $\pm 2$  days) of each cycle for cycles 1, 2, and 3 will be repeated by baseline HSV-1 serostatus (i.e., seropositive and seronegative) among subjects with known HSV-1 status at baseline. The difference in clearance rate at Day 8 for cycles 1, 2, and 3 will be provided. The corresponding 95% confidence interval will be based on the Wilson's score method with continuity correction ([Newcombe, 1998](#)).

### **Rate and Subject Incidence of Talimogene Laherparepvec DNA Detection and Viral Detection on the Exterior of Occlusive Dressing**

The subject incidence of positive qPCR and subsequent positive plaque testings will be evaluated from swabs of occlusive dressings. The number and proportion of subjects who have at least 1 positive qPCR result from the exterior of occlusive dressing swabs and the number and proportion of subjects exhibiting detectable virus from subsequent plaque testings will be presented. Numeric results of positive qPCR, and separately for positive plaque analysis, will be summarized as a continuous variable.

A detailed listing of qPCR and subsequent plaque results for subjects having a positive qPCR testing will be provided.

The analysis of this endpoint will be based on the Exterior of Occlusive Dressing Evaluable Analysis Set.

### **Rate and Subject Incidence of Talimogene Laherparepvec DNA Detection and Viral Detection at the Skin Surface of Injections**

The subject incidence of positive qPCR and subsequent positive plaque assays will be evaluated from swabs of skin surface of injections. The number and proportion of subjects who have at least 1 positive qPCR result from at the skin surface of the injected

lesions and the number and proportion of subjects exhibiting detectable virus from subsequent plaque testings will be presented. Numeric results of positive qPCR testings, and separately for positive plaque analysis, will be summarized as a continuous variable.

A detailed listing of qPCR and subsequent plaque results for subjects having a positive qPCR testing will be provided.

Analysis of this endpoint will be based on the skin surface of the Injected Lesion Evaluable Analysis Set.

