- ^v Swabs of oral mucosa: During treatment swabs of oral mucosa for qPCR testing of talimogene laherparepvec DNA with or without TCID50 assay for talimogene laherparepvec virus will be collected at the following visits: Week 1 and 4 prior to talimogene laherparepvec administration and 7 (\pm 2) days and 14 (\pm 2) days following talimogene laherparepvec administration; Week 7 prior to talimogene laherparepvec administration. During safety follow-up, swabs of oral mucosa will be collected at the 30 (+ 7) day safety follow-up visit for qPCR testing of talimogene laherparepvec DNA.
- ^w Swabs of any lesion suspected to be herpetic in origin (if any) will be collected during treatment and safety follow-up as follows: subject should return to clinic within 3 days of the occurrence of reportable lesion suspected to be herpetic in origin such as cold sores or vesicles. The lesion should be evaluated by the investigator and swabbed if HSV infection is suspected. The sample will be sent to the central laboratory for detection of talimogene laherparepvec DNA using qPCR testing.

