### **Rate of Talimogene Laherparepvec DNA Detection and Viral Detection at the Skin Surface of Injection**

The rate of detectable talimogene laherparepvec DNA per qPCR at the skin surface of injected lesions is defined as the number of cases of detectable talimogene laherparepvec DNA per qPCR divided by all swabs collected at the skin surface of injected lesions per time point. The rate of viral detection in injected lesions is defined as the number of cases of detectable talimogene laherparepvec virus (TCID50 positive) divided by the number of swabs collected at the skin surface of injected lesions per time point.

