### **Rate of Talimogene Laherparepvec DNA Detection and Viral Detection in Oral Mucosa**

The rate of detectable talimogene laherparepvec DNA per qPCR in oral mucosa is defined as the number of cases of detectable talimogene laherparepvec DNA per qPCR divided by all swabs collected in oral mucosa per time point. The rate of viral detection in oral mucosa is defined as the number of cases of detectable talimogene laherparepvec virus (TCID50 positive) divided by the number of swabs collected in oral mucosa per time point.

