#### **6.9 Skin Surface of Injections Evaluable Analysis Sets**

Subjects who are enrolled, receive at least one dose of talimogene laherparepvec, and have at least one swab collected from the skin surface of injections. This analysis set is used to examine the detection of talimogene laherparepvec DNA and virus at the skin surface of in injections.

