## **6.11 Lesion Analysis Sets**

The Injected Lesion Analysis Set includes any target lesion and new measurable lesion that was ever injected and the uninjected lesion analysis set includes any target lesion and new measurable lesion that was never injected among subjects in Full Analysis Set. The Injected Lesion Evaluable and Uninjected Lesion Evaluable analysis sets will include the corresponding subset of target lesions and new measurable lesions with at least one post-baseline measurement prior to a censoring event, ie, non-study anticancer therapy, merged with another lesion, or resection (except if it is partial or complete resection and pathology indicates absence of malignant cells). If a lesion splits, the sum of the length of the split lesions will be added together prior to analysis.

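### SAP 9.6.2 names a tumour-measurement lesion set for injection-site shedding instead of the swab set in SAP 6.9, and the oral virus rate does not exclude the safety follow-up swab, which is tested by qPCR only

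*SAP*

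**What the plan says.** **Injection site.**

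- The skin-surface part of SAP 9.6.2 reports the number and proportion of subjects with a positive qPCR swab and with detectable virus. It then fixes the population: "Analysis of this endpoint will be based on the skin surface of the Injected Lesion Evaluable Analysis Set".
- SAP 6.11 defines that set within the Full Analysis Set as, among injected lesions, the "corresponding subset of target lesions and new measurable lesions with at least one post-baseline measurement prior to a censoring event". The censoring events are other anticancer therapy, merging with another lesion, and resection (unless pathology shows no malignant cells).
- SAP 6.9 defines a different, subject-level set: enrolled and dosed subjects who "have at least one swab collected from the skin surface of injections". Its stated purpose is this endpoint; it is "used to examine the detection of talimogene laherparepvec DNA and virus at the skin surface of in injections".
- SAP section 5 defines the per-sample viral rate at the injection site as positives "divided by the number of swabs collected at the skin surface of injected lesions per time point".

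**Oral mucosa.**

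- SAP section 5 defines the viral-detection rate as TCID50-positive cases "divided by the number of swabs collected in oral mucosa per time point".
- Protocol 7.2.2 sends on-treatment oral swabs to TCID50 when qPCR is positive. At the end of treatment the Part 2 schedule says only that "swabs of oral mucosa will be collected at the 30 (+ 7) day safety follow-up visit for qPCR testing of talimogene laherparepvec DNA". The Part 1 schedules and the synopsis agree.
- SAP 6.10 gives DNA detection as the purpose of the oral swab set, whereas SAP 9.6.2 uses that set for virus as well.

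**The concern.** Shedding bears on transmission to household members, caregivers and staff, so its denominators should consist of people and samples that were tested for it. Two places in the SAP do not secure this.

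The injection-site endpoint is tied to whether a lesion was measured again for tumour response. That condition has nothing to do with whether virus was on the skin. A programmer who follows 9.6.2 as written would build a table whose unit does not match the statistic and whose membership depends on tumour follow-up.

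The oral virus rate has no stated list of time points. If safety follow-up is tabulated with the rest, the table would show no infectious virus at a visit for which no virus assay is scheduled.

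**Working it through.** The plan gives no figure to reproduce here. The check compares definitions and counts scheduled times.

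**1. Unit and conditions.** SAP 9.6.2 wants a proportion of subjects and section 5 wants a proportion of swabs. SAP 6.11 supplies lesions, so it fits neither. SAP 6.9 supplies subjects with a swab, with no size or scan condition. The dressing and oral parts of 9.6.2 each cite their own swab set (6.8 and 6.10). Only the skin-surface part does not, which leaves the 6.9 set without a use.

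**2. Swab times against the first scan.** Take day 1 as first dose with 21-day cycles: Week 4 = day 22, Week 7 = day 43, Week 10 = day 64.

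- First scheduled scan: Week 10 ± 1 week, so days 64 − 7 = 57 to 64 + 7 = 71.
- Part 2 injection-site swabs: days 1, 8, 15, 22, 29, 36, 43. That is 7 times, all before day 57.
- Part 1 injection-site swabs: days 1, 2, 3, 8, 15, 22, 23, 24, 29, 36, 43, 50, 64. That is 13 times, 12 of them before day 57.

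A subject can therefore complete the Part 2 swab schedule before any scheduled post-baseline scan.

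**3. Which early leavers still get a measurement.** The schedule footnotes require imaging at safety follow-up if there is no confirmed PD and no scan within 9 (± 1) weeks. Follow-up is 30 to 37 days after the last dose (both drugs assumed to stop together). The baseline scan is at most 28 days before enrolment, and first dose at most 5 days after it.

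- Youngest baseline scan, in weeks = (last dose day + 30)/7.
- Oldest = (last dose day + 37 + 28 + 5)/7.

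| Doses | Last dose day | Age of baseline scan at follow-up (weeks) |
|---|---|---|
| 1 | 1 | 31/7 = 4.4 to 71/7 = 10.1 |
| 2 | 22 | 52/7 = 7.4 to 92/7 = 13.1 |
| 3 | 43 | 73/7 = 10.4 to 113/7 = 16.1 |

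Most subjects stopping after one dose need no new scan. Many stopping after two doses do, and so do all stopping after three without confirmed PD. Protocol 7.2.2 also asks for caliper measurement of skin and palpable nodal lesions at dosing; SAP 6.11 does not say whether these count.

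**4. Lesion size.** Protocol Appendix D makes lesions under 10 mm non-measurable, and measurable lesions beyond the target limit non-target. Table 4 allows Part 2 injection of lesions down to the row below 0.5 cm. Such lesions can be injected and swabbed but cannot enter the 6.11 set. The subject remains if another injected lesion qualifies. Part 1 injected liver tumours only, so the skin-lesion effect is confined to Part 2.

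**5. Oral virus at safety follow-up.** With no TCID50 scheduled, the numerator is 0 for any number N of swabs. The exact 95% upper limit for 0/N is 1 − 0.025^(1/N): 30.8% for N = 10, 16.1% for 21, 6.7% for 53 (Part 2 enrolment) and 2.9% for 127 (total enrolment). The SAP specifies no interval for oral swabs. The limits only show how much reassurance a reader could wrongly take from such a zero.

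**The case against.** The best defence is that the skin-surface sentence is a wrong cross-reference and not a chosen analysis. Its wording matches no defined set, 6.9 exists for this purpose, section 5 counts all swabs, and the neighbouring endpoints cite the right sets. That is probably so. It explains the error, but the instruction as it stands is still the wrong one.

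A reader might infer that every early leaver is excluded. The documents do not support that: 6.11 asks for any post-baseline measurement, not the Week 10 scan. Subjects with the fullest swab record are those most likely to have a follow-up scan, and confirmed PD already implies later measurements. Those lost are mainly subjects who also miss follow-up, or who stop so early that no new scan is due and no caliper measurement counts.

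A reader might also estimate the loss from the 6% of subjects without post-baseline assessment in the pembrolizumab HCC trial cited in Protocol 2.5.1: 0.06 × 53 = 3.2 subjects. That rate comes from one tumour type on another regimen, while five of the six Part 2 arms are not HCC. It does not measure how many swabbed subjects here would lack a lesion measurement.

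On the oral rate, the SAP names safety follow-up as a time point for blood and urine but not for oral virus. It also plans a listing of qPCR and subsequent virus results, in which an untested follow-up positive would be visible. Both points stand, so the 0/N result is conditional and not a certainty.

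Finally, because 6.8 to 6.10 do not ask for a post-dose swab, a reader might infer that all three admit subjects with only a pre-dose sample. For dressings (6.8) this has no effect, since every scheduled dressing swab follows a dose. For 6.9 and 6.10 it is possible but minor.

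**Conclusion.** The concern holds as an internal contradiction in the SAP. For injection-site shedding, 9.6.2 names a set with the wrong unit and irrelevant entry conditions, against 6.9 and section 5. Read literally, it drops some swabbed subjects with no later lesion measurement and, in Part 2, swabs from injected lesions that are non-target or under 10 mm. The documents do not allow the number to be derived.

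The oral virus rate is under-specified. If it is tabulated at safety follow-up it is 0/N whatever the truth; because the rate is per time point, on-treatment rates are unaffected.

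The day counts assume visits on schedule and 21-day cycles. These are descriptive secondary safety summaries with no hypothesis test, and the primary ORR analysis does not depend on them.

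**What to change.** - In the skin-surface part of SAP 9.6.2, cite the Skin Surface of Injections Evaluable Analysis Set (6.9).
- In SAP section 5, restrict the oral viral-detection rate to on-treatment time points. At safety follow-up give the qPCR rate only and report virus as not assessed.
- In SAP 6.10, add virus to the stated purpose, to agree with 9.6.2.
- Optionally, require at least one post-dose swab in 6.9 and 6.10, as 6.6 does for blood and urine. This is not needed in 6.8.

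The cost is a few lines of SAP text before programming. No data collection changes, and the only output lost is a follow-up virus rate with no scheduled assay behind it.

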### **Rate and Subject incidence of Talimogene Laherparepvec DNA Detection and Viral Detection in Oral Mucosa**

The subject incidence of positive qPCR and subsequent positive plaque assays will be evaluated from swabs of oral mucosa. The number and proportion of subjects who have at least 1 positive qPCR result from oral mucosa and number and proportion of subjects exhibiting detectable virus from subsequent plaque testings will be presented. Numeric results of positive qPCR, and separately for plaque analysis, will be summarized as a continuous variable.

A detailed listing of qPCR and subsequent plaque results for subjects having a positive qPCR testing will be provided.

Analysis of this endpoint will be based on the Oral Mucosa Evaluable Analysis Set.

### **Rate and Subject Incidence of Detectable Talimogene Laherparepvec DNA per qPCR in Suspicious Lesions to be Herpetic in Origin**

This rate will be calculated based on the Reactive Swab Analysis Set.

The subject incidence will be reported for positive qPCR for talimogene laherparepvec DNA detection in any swab of a lesion suspected to be herpetic in origin. The analysis will be based on the Reactive Swab Analysis Set. A detailed listing of qPCR results for subjects having a positive qPCR testing will be provided. In addition, a listing for all subjects in the Reactive Swab Analysis Set will be provided with reported treatment-emergent adverse events (including preferred term, verbatim term, start and end dates, duration, grade, seriousness, and relationship to IP), and qPCR result (Y/N).

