10. STATISTICAL CONSIDERATIONS

10.1 Study Endpoints, Analysis Sets, and Covariates

10.1.1 Study Endpoints

Primary Endpoint:

Part 1:

Monotherapy cohorts 1-4: Subject incidence of DLTs with intrahepatic injection of talimogene laherparepvec into liver tumors in subjects with non-HCC with liver metastases and subjects with HCC without active viral hepatitis.

Combination cohorts 5 and 6: Subject incidence of DLTs with intrahepatic injection into liver tumors of talimogene laherparepvec in combination with systemic IV administration of pembrolizumab in subjects with non-HCC with liver metastases and subjects with HCC with and without viral hepatitis.

Part 2:

- ORR per modified irRC-RECIST with intralesional injection of talimogene laherparepvec into cutaneous, subcutaneous, lymph node, and liver tumors in combination with systemic IV administration of pembrolizumab separately by tumor type arm (hormone receptor positive BC, TNBC, CRC, CSCC, BCC, and HCC with and without viral hepatitis)
- Subject incidence, for each tumor type arm, of treatment-emergent and treatment-related adverse events, including DLTs

Secondary Endpoint(s):

Efficacy:

Part 1:

- ORR, BOR, DRR, DOR, response in injected and uninjected lesions, DCR, PFS, and OS separately for non-HCC and HCC tumors in monotherapy and combination cohorts

Part 2:

- BOR, DRR, DOR, response in injected and uninjected lesions, DCR, PFS, and OS by primary tumor type arm (hormone receptor positive BC, TNBC, CSCC, CRC, BCC, and HCC with and without viral hepatitis)

Safety:

Parts 1 and 2:

- Subject incidence of treatment-related and treatment-emergent adverse events in each monotherapy and combination cohorts in Part 1 and each tumor type separately in Part 2, and HCC with and without viral hepatitis in Part 2
- Subject incidence of detectable talimogene laherparepvec DNA in blood and urine

- Incidence of clearance of talimogene laherparepvec DNA from blood and urine
- Subject incidence (per subject) and rate of detection (per sample) of talimogene laherparepvec DNA and virus at the surface of injection site, the exterior of the occlusive dressing, and the oral mucosa
- Subject incidence of talimogene laherparepvec DNA detection in lesions suspected to be herpetic in origin

Exploratory Endpoint:

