### **Rate of Detectable Talimogene Laherparepvec DNA per qPCR in Suspicious Lesions to be Herpetic in Origin**

The rate of detectable talimogene laherparepvec DNA per qPCR in suspicious lesions is defined as the number of cases of detectable talimogene laherparepvec DNA per qPCR from swabs collected from lesions that are suspected to be herpetic in origin divided by all swabs collected from these lesions per time point.

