## **6.5 Reactive Swab Analysis Set**

Subjects who are enrolled, receive at least one dose of talimogene laherparepvec, and have at least one swab sample collected from lesions that are suspected to be herpetic in origin. This analysis set is used to examine the number of subjects with a lesion suspected to be herpetic, and detection of talimogene laherparepvec DNA by qPCR in lesions suspected to be herpetic in origin.

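### The subject incidence of talimogene laherparepvec DNA in suspected herpetic lesions is planned among swabbed subjects only, so it is swab positivity and not incidence among treated subjects

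*SAP*

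**What the plan says.** Protocol 10.1.1 lists as a secondary safety endpoint, for both parts: "Subject incidence of talimogene laherparepvec DNA detection in lesions suspected to be herpetic in origin". SAP 2.1 repeats it.

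Swabbing is driven by events. The footnotes to the schedules in Protocol 7.1 ask the subject to return within 3 days of a suspicious lesion, and then: "The lesion should be evaluated by the investigator and swabbed if HSV infection is suspected".

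The SAP treats the endpoint in three places:

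- **SAP 5** defines a per-swab rate, in which positive swabs are "divided by all swabs collected from these lesions per time point".
- **SAP 6.5** defines the Reactive Swab Analysis Set as enrolled subjects given talimogene laherparepvec who "have at least one swab sample collected from lesions that are suspected to be herpetic in origin". It adds: "This analysis set is used to examine the number of subjects with a lesion suspected to be herpetic".
- **SAP 9.6.2** says of the rate: "This rate will be calculated based on the Reactive Swab Analysis Set". It then plans a subject incidence, counting subjects with a positive result on any such swab, and says: "The analysis will be based on the Reactive Swab Analysis Set".

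The general rules name a different set. The statistical paragraphs of the Protocol Synopsis assign safety analyses in both parts to the safety analysis set, and the same paragraph includes the qPCR summary of these swabs. SAP 9.1 gives the Safety Analysis Set to safety endpoints other than DLT. SAP 10 records no change from the protocol.

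**The concern.** An incidence normally has everyone at risk in its denominator. Here a subject enters the denominator only after a lesion has appeared and raised suspicion of HSV. The planned proportion therefore answers this question: of the subjects swabbed, how many were positive? The label invites a reader to take it as the answer to another: of the subjects treated, how many had a DNA-positive lesion?

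The per-swab rate is also a positivity measure. The plan as written thus yields two positivity figures and no incidence among treated subjects for this secondary safety endpoint. In a small Part 2 arm with a single swabbed subject, the reported subject incidence could only be 0% or 100%.

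**Working it through.** The documents state no expected value for this endpoint, so there is no planned figure to reproduce. The check is on the denominator.

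**Inputs**

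- x = subjects with any positive reactive swab (numerator, SAP 9.6.2). Not given.
- m = subjects in the Reactive Swab Analysis Set (SAP 6.5). Not given.
- N = subjects treated with talimogene laherparepvec. Protocol 3.3 gives 127 enrolled (74 in Part 1, 53 in Part 2). This is an enrolled count, so it is an upper bound for N.

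**Formulas**

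- Planned figure: x/m.
- Incidence among treated subjects: x/N.
- Ratio: (x/m) / (x/N) = N/m, for x > 0.

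Since m cannot exceed N, the ratio is at least 1. It equals 1 only if every treated subject is swabbed. The direction follows from the definitions alone.

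**Illustration (m assumed)**

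| Assumed m | N/m, N = 127 | N/m, N = 53 (Part 2) |
|---|---|---|
| 5 | 127/5 = 25.4 | 53/5 = 10.6 |
| 10 | 127/10 = 12.7 | 53/10 = 5.3 |
| 20 | 127/20 = 6.35 | 53/20 = 2.65 |
| 40 | 127/40 = 3.2 | 53/40 = 1.3 |

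As proportions, with x also assumed and Clopper-Pearson 95% intervals:

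- N = 127, m = 10, x = 2: planned 2/10 = 20.0% (2.5 to 55.6); per treated subject 2/127 = 1.6% (0.2 to 5.6).
- N = 127, m = 40, x = 8: planned 8/40 = 20.0% (9.1 to 35.6); per treated subject 8/127 = 6.3% (2.8 to 12.0).
- N = 53, m = 10, x = 2: planned 2/10 = 20.0% (2.5 to 55.6); per treated subject 2/53 = 3.8% (0.5 to 13.0).

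The first two rows give the same planned figure for per-treated incidences that differ four-fold (8/127 against 2/127).

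**Comparison with the related endpoints.** The sets for blood, urine, occlusive dressing, skin surface and oral mucosa (SAP 6.6 and 6.8 to 6.10) also require a sample. Those samples are scheduled for every treated subject, so entry does not depend on the event being measured. Entry to the Reactive Swab Analysis Set does.

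**The case against.** **What the other side can say, and what stands.** Denominators restricted to subjects with a sample are the SAP's convention for its shedding and biodistribution endpoints, and the clearance sets in SAP 6.7 even require an earlier positive sample. It would be wrong to infer that every other subject incidence in the safety section is taken over all treated subjects. The distinction that survives is between scheduled and event-triggered sampling. Clearance, for its part, is conditional by nature.

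The endpoint wording can also be read as detection among subjects who have such lesions. Read so, x/m is a valid quantity, and the SAP names its analysis set openly. It overstates only when taken as risk per treated subject. SAP 9.6.2 lists every subject in the set with the qPCR result, so a reader of the report could work out x/N.

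**Stronger readings that the documents do not support.**

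- A reader might infer that the share of subjects with a suspected lesion will be reported as 100%. SAP 6.5 speaks of a number of subjects, and a count is unaffected by the denominator.
- A reader might infer that arms cannot be compared because swabbing practice differs between them. The swabbing trigger is worded alike in the monotherapy and combination schedules, and nothing says that practice differs. If it did, x/N would suffer too.
- A reader might take the 25-fold factor as an estimate. It rests on an assumed m of 5, and 127 is an enrolled count that pools parts which are summarised separately.
- A reader might fault the sentence on the rate. It concerns the per-swab measure of SAP 5, for which this set is right.

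**Conclusion.** The point holds in a limited form. The figure that SAP 9.6.2 will call subject incidence is positivity among swabbed subjects. It exceeds the incidence per treated subject by N/m whenever there is at least one positive subject and not everyone treated is swabbed. The direction is certain. The size is unknown, because m is not in the documents; the illustrated factors run from 25.4 down to 1.3 across the assumed m and the two values of N.

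Taken literally, the choice also departs from the Synopsis and SAP 9.1 on the set for safety endpoints, while SAP 10 records no change. The consequence is confined to how one secondary safety endpoint is reported and labelled. No decision rule, dose decision or primary analysis uses it.

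**What to change.** In the SAP 9.6.2 paragraph on suspected herpetic lesions:

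1. Report, by cohort in Part 1 and by tumor type arm in Part 2, the subject incidence of (a) a suspected lesion that was swabbed and (b) a DNA-positive lesion. Use as denominator the Safety Analysis Set subjects who received one or more doses of talimogene laherparepvec. The dose condition is needed because SAP 6.2 also admits subjects in the combination cohorts and Part 2 who received only pembrolizumab.
2. Keep the Reactive Swab Analysis Set for the per-swab rate of SAP 5.
3. If x/m is kept, label it as positivity among swabbed subjects and show x and m.

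The cost is a wording change and one extra table column, with no new data. There is one small downside: a suspected lesion that was never swabbed counts as a non-event in x/N, which may then understate. Report the number of such lesions where it is known.
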